7.2. Methods and terms of evaluation, reporting and analysis of efficacy parameters

Periodicity of the procedures and assessments is also provided in Schedule of visits and procedures (see Table 1).

Blood sampling to determine concentration of hsCRP and level of brain natriuretic peptide (BNP, NT-pro-BNP) will be made at Visit 1 Day 1 (at baseline), Visit 2 (Day 3), Visit 3 (Day 14±3) and Visit 4 (Day 28±3) of the study. In addition, blood sampling to determine level of brain natriuretic peptide (BNP, NT-pro-BNP) will be made at Visit 6 (Month 12±2 weeks) of the study. Concentration of hsCRP and level of brain natriuretic peptide (BNP, NT-pro-BNP) will be determined in central laboratory.

Throughout the clinical study, the investigator will follow the subjects to evaluate and record cardiovascular and other outcomes (fatal outcomes, hospitalizations¹, new HF) based on the current clinical recommendations and terminological criteria "2017 Cardiovascular and Stroke Endpoint Definitions for Clinical Trials" (Hicks K.A. et al., 2018) (see Attachment 1).

Echo-CG will be carried out at Visit 1 (Day 1) (this procedure is permitted to be done within 24 hours from the moment of randomization), Visit 4 (Day 28±3) and Visit 6 (Month 12±2 weeks) by qualified personnel of the study site using relevant diagnostic equipment. Measurements will be carried out in accordance with the internal document on the interpretation of echo-CG findings. Echo-CG parameters assessed during the study are described in detail in the Statistical Analysis Plan. Given that Echo-CG is an operator-dependent technique, assessment and recording echo-CG results will be centralized.

The following information will be collected upon dose change, dosing scheme modification or product discontinuation in concomitant therapy: date of change, description of change (discontinuation, dose escalation, dose reduction, switch to another product of another group), cause of changes (improved condition, aggravated condition, adverse events/adverse reactions associated with the study product).

8. Safety evaluation

8.1. List of safety parameters

Safety endpoints:

- 1. Incidence of AE/SAE during the study.
- 2. Changes in physical examination (including body weight), vital signs during the study.

¹Hospitalization due to HF will also include cases of prolongation of current hospitalization for the treatment of ST segment elevation MI if HF has developed within 24 hours following hospital admission

CONFIDENTIAL

Translation dated 27-Oct-2021

based on Russian Version 4.0 dated 02-Oct-2021

Page 56 of 98

8.2. Methods and terms of evaluation, registration and analysis of safety parameters

8.2.1. General provisions

Safety assessment will include monitoring all recording all AEs and SAEs according to MedDRA and Common Terminology Criteria for Adverse Events (CTCAE v.5.0.).

The unblinded medical monitor will receive and evaluate all AE reports on a regular basis during the study.

Monitoring will include physical examination including vital signs, hematology, serum chemistry as outlined in Schedule of visits and procedures (see Table 1).

8.2.1.1. Physical examination

Physical examination will be carried out at Visit 1 (Day 1), Visit 2 (Day 3), Visit 3 (Day 14±3), Visit 4 (Day 28±3) and Visit 6 (Month 12± 2 weeks) and will include the assessment of the following: general condition, injection site, condition of skin, musculoskeletal system, lymph nodes, thyroid gland, upper and lower respiratory tract, heart, vessels, abdominal organs, kidneys, psychoneurological status. Abnormal values reported at the screening visit will be recorded in eCRF section "Co-morbidities". At the following visits, "Adverse Events" section of eCRF will include only abnormal values/changes relative to screening physical examination values meeting AE definition.

Weight measurement will be carried out at Visit 1 (Day 1) or Visit 2 (Day 3), Visit 3 (Day 14± 3), Visit 4 (Day 28±3) and Visit 6 (Month 12±2 weeks). Based on severity of the subject's condition, body weight will be measured in recumbent condition at Visit 1 Day 1 using hospital bed or, if not available, at Visit 2 (Day 3) in standing position using the relevant balance. At the remaining visits, measurement will be done in standing position using the relevant balance.

Height measurement will be done in a standing position at Visit 3 (Day 14±3) or at any time during the hospitalization (it is permissible to record any value obtained during the hospitalization, when it is possible to measure the patient's height).

Vital signs will be measured at Visit 1 (Day 1) or Visit 2 (Day 3), Visit 3 (Day 14±3), Visit 4 (Day 28±3), Visit 6 (Month 12±2 weeks). Based on severity of the subject's condition, vital signs will be measured in recumbent position or sitting position after a 5-min rest. Systolic and diastolic BP will be measured on the same arm using the same device. HR will be measured on the apex of heart using phonendoscope. HR and RR will be measured for 1 min. Body temperature will be taken by the axillary route.

8.2.1.2. Laboratory examination

Hematology and biochemistry will be made at Visit 1 (Day 1) (baseline), at Visit 3 (Day 14±3) and Visit 4 (Day 28±3) in central laboratory. At Visit 1 determination of the absolute neutrophil count is performed in the local laboratory of the site to assess the inclusion/exclusion criteria.

Hematology will include the following parameters: hemoglobin, erythrocyte count, leukocyte count, leukogram with obligatory measurement of absolute neutrophil count, platelet count.

Biochemistry will include the following parameters: hepatic chemistry values (AST, ALT, GGT, AP, LDH, total bilirubin, direct bilirubin, indirect bilirubin), renal chemistry values (serum creatinine, serum urea/urea nitrogen [BUN]), serum electrolytes (sodium, potassium, chlorides), CPK, CPK-MB.

Results of laboratory tests performed within 12 hours before randomization may be used for the study eligibility assessment.

8.2.2. Adverse event determination

An adverse event - AE - is any untoward medical event arising after administration of the study product regardless of causality. An AE can therefore be any unfavorable and unintended sign (including an abnormal laboratory finding, for example), symptom, or disease temporally associated with the use of a medicinal product, whether or not considered related to the medicinal product.

AEs include (but not limited to) the following:

- Laboratory values outside normal range having clinical relevance.
- Pre-existing findings at physical examination which aggravated compared to baseline and are considered clinically relevant.
- Physical examination findings (including vital signs) considered clinically relevant.

8.2.3. Adverse events of interest

The following safety concerns have been identified as Adverse Events of Special Interest (AESIs) based on the safety data currently available for RPH-104 and IL-1 inhibitor biologics:

- Infections (including serious infections), including tuberculosis and opportunistic infections
 - Confirmed cases of active tuberculosis should also be documented as SAEs;
- Malignant neoplasms
 - The investigator will be asked to provide relevant medical information/documentation (i.e. the results of pathological/histological examination) for all cases of malignant neoplasms, regardless of their seriousness, as these cases are subject to entry into the safety database;
- Increased blood lipids (i. e., hypercholesterolemia, increased blood cholesterol, increased blood triglycerides, hypertriglyceridemia, and increased LDL cholesterol);
- Systemic reactions to drug administration and hypersensitivity reactions;
- Neutropenia, thrombocytopenia, leukopenia;
- Drug-induced liver injury, any liver enzyme increase;
- Injection site reactions.

All of the above events are subject to recording and analysis as AESIs.

8.2.3.1. Emergency

Given that in rare cases anaphylactic and anaphylactoid reactions are possible during the product administration, the study site should dispose of the relevant medicines and equipment for urgent medical assistance including antishock therapy. Development of such urgency and measures taken should be recorded on the relevant pages of eCRF.

8.2.4. Reporting about adverse events

The investigator and study site personnel will be responsible for detection, relevant medical assistance, documentation and reporting of cases meeting AE and SAE definition.

Information on AEs will be collected since signing ICF and until the study completion by the subject. SAEs will be recorded since signing ICF and for up to 30 days after the study product treatment discontinuation or until the last visit whichever is the latter. AEs recorded prior to the study product administration will be added to eCRF section "Medical history".

The investigator should document all the AEs during the study in case histories and eCRFs.

Adverse events will be recorded based on complaints reported by the subjects themselves, results of interviews between investigator and subject, results of physical examination and laboratory tests. The investigator should formulate his questions to the subject in the manner not provoking the subject to report unreliable information.

AEs will be recorded in the relevant eCRF sections as well as in source medical documents of the subject.

The following information should be specified when recording adverse events:

- Subject identification number;
- Nature of AE (preferably diagnosis rather than the list of symptoms);
- Date of AE onset and resolution (and time if applicable);
- Measures related to AE;
- AE meeting SAE criteria;
- AE severity;
- AE meeting unexpected AE criteria;
- Relationship between the AE and study product administration (according to the investigator);
- Outcome of AE.

8.2.5. Definition of a serious adverse event

A serious adverse event - SAE - is defined as any untoward medical occurrence that:

- Resulted in death;
- Was life-threatening;
- Resulted in permanent or pronounced incapacity or disability;
- Required hospitalization or its prolongation;
- Resulted in a birth defect/congenital abnormality in children of patients who had been treated with the drug.
- Furthermore, serious adverse events include any event not meeting the criteria above though being a relevant medical event according to the investigator.

Any other AEs not meeting these criteria will be rated as non-serious.

8.2.6. Serious adverse event reporting

To assure safety of the subjects in case of any SAE development after signing ICF and until the end of the study, regardless of suspected causes of SAE or association with the study product, SAE should be reported to Sponsor within 24 hours after the investigator became aware of the SAE.

If a subject has a SAE considered to be related to the study product, a report thereof should be submitted even in case the study has been terminated already.

Filling serious adverse event report form

SAEs should be reported by filling out the SAE page in the eCRF within 24 hours from the time the investigator finds out about the SAE. In the event that access to the eCRF is temporarily impossible, the center has the opportunity to report the SAE by sending a scan of the hard copy of the serious adverse event report by email to

[contact]

or by [contact]

The investigator must notify the Local Ethics Committee (LEC)/Institutional Review Board (IRB) on the SAE according to LEC/IRB standard operation procedures.

8.2.7. Definition of unexpected adverse events

An unexpected AE in its nature or severity is inconsistent with the ones outlined in the current Investigator's Brochure.

Any other AEs are considered to be expected.

8.2.8. Submission of reports on suspected unexpected adverse reactions (SUSAR)

The study sponsor should notify regulatory authorities on all suspected unexpected serious adverse reactions (SUSARs) within the terms specified by laws. In context of notification of regulatory authorities and investigators, the SUSARs will mean unexpected SAEs considered by the investigator and/or Sponsor as related to the study product.

8.2.9. Adverse event severity assessment

AE severity will be evaluated according to CTCAE v5.0 classification. If an AE is lacking in CTCAE classification, it will be classified based on the following grading:

Grade 0: No AE

Grade 1: Mild; asymptomatic or mild symptoms; clinical or diagnostic observations only; intervention not indicated.

Grade 2: Moderate; minimal, local or noninvasive intervention indicated; limiting age appropriate instrumental activities of daily living.²

² Limitation of age-appropriate self-care includes cooking, purchasing goods and clothes, using phone, money management, etc.

CONFIDENTIAL

Translation dated 27-Oct-2021

based on Russian Version 4.0 dated 02-Oct-2021

Page 60 of 98

Grade 3 Severe or medically significant but not immediately life-threatening; hospitalization or prolongation of hospitalization indicated; disabling; limiting self-care activities of daily living.³

Grade 4 Life-threatening consequences; urgent intervention indicated.

Grade 5 Death related to AE.

Severe AE is not necessarily serious by nature and SAE is not necessarily severe by definition.

8.2.10. Adverse event outcome evaluation

AE outcome will be determined as follows:

Fatal:	The subject died due to AE (death is an outcome, not an AE)
Recovering/Resolving	Reduced intensity of AE
Not Recovered/ Not Resolved (Continuing)	AE did not resolve, intensity unchanged
Recovered/Resolved with Sequelae	AE resolved but with a permanent defect.
Recovered/Resolved	AE resolved completely without sequelae
Unknown:	AE outcome is unknown as the subject did not attend the follow-up visit and attempts to obtain the follow-up information were useless (loss to follow-up)

8.2.11. Relationship between an adverse event and study drugs

The investigator will be responsible to assess causality between the AE and study product administration (related/unrelated). The investigator should use his knowledge on the subject, circumstances of the event and evaluation of any potential alternative causes to determine whether the AE is related to the study product or not. One of the following options should be chosen for relationship between AE and the study product: "related" or "unrelated". The following recommendations should be taken into account:

- relationship between AE development and initiation of the study product administration;
- AE changes over time after discontinuation of the study product;
- known relationship between the study product or similar treatments;
- risk factors increasing the risk of AE;
- any non-treatment-related factors associated with the event frequency.

The investigator should report relationship of every event with the study product based on the most probable relationship assessment, at that the study site personnel will be responsible to obtain any lacking data.

³Limitation of self-care includes bathing, dressing and undressing, using the toilet, taking medications, but not bedridden.

CONFIDENTIAL

Translation dated 27-Oct-2021

based on Russian Version 4.0 dated 02-Oct-2021

Page 61 of 98

If relationship assessment changes over time due to new or modified information, it may be revised.

8.2.12. Follow-up of adverse events

All AEs should be monitored until their resolution or stabilization.

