5.4.2. Early withdrawal criteria

The subject may withdraw the study at any time before its termination (Visit 6). The investigator may also decide to withdraw a subject at his/her own discretion.

The reasons for study withdrawal will be reflected in source medical documents and eCRF and may include the following:

1. Recall of informed consent to participate in the study.
2. Serious or intolerable AE requiring withdrawal from the study at the investigator's discretion.
3. Investigator's decision that continuation of the study participation contradicts the subject's interests.
4. Investigator's decision if the subject does not follow the study procedures and/or Protocol.
5. Protocol deviation which, according to the investigator, requires early subject withdrawal from the study (e.g. necessity or performance of additional therapy forbidden by the Protocol). In this case, decision on the subject withdrawal will be agreed with Sponsor.
6. Study termination by Sponsor.
7. Study termination by regulatory authorities.
8. Pregnancy of the subject.
9. Death of the subject.

5.4.3. The list of data by early withdrawn subjects and terms of their collection

In case of early withdrawal, justification of such decision and its reason should be specified in source medical documents and eCRF.

Where a subject recalls his/her informed consent, the investigator should try to learn the cause of such a decision.

In case of early withdrawal at the follow-up period post dosing (Visit 1 Day 1 – Visit 4 Day 28) an early withdrawal visit is advised including Visit 4 procedures.

In case of early withdrawal during additional clinical follow-up period (Day 29 – Visit 6 Month 12) an early withdrawal visit is advised including Visit 6 procedures.

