5.4.5. Follow-up of withdrawn subjects

Follow-up of the subjects withdrawn due to a SAE will be performed until its resolution or stabilization.

The subjects withdrawn for other reasons will not be followed.

6. Treatment of the study subjects

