6.2.2. Forbidden concomitant therapy

During the study, the following medicinal products will be forbidden in the terms specified:

- biological (except for RPH-104) including but not limited to: tocilizumab, rituximab, TNF α inhibitors [Visit 1 Day 1 - Visit 4 Day 28];
- immunosuppressants [Visit 1 Day 1 – Visit 4 Day 28] including but not limited to:
 - corticosteroids at doses of >1 mg/kg of methylprednisolone equivalent orally as well as systemic, except for intravenous (i.v.) ones for acute allergic reactions;
 - cyclosporine A, methotrexate etc.;
- colchicine [Visit 1 Day 1 – Visit 4 Day 28];
- anakinra, canakinumab, rilonacept [Visit 1 Day 1 – Visit 6 Month 12];
- immunization with live vaccines within 90 days prior to or after the study product administration;
- any experimental products.

NSAIDs are not forbidden.

6.2.3. Use of the medicinal products not allowed or not provided for by the Protocol

If a life- or health-threatening situation took place during the study and the subject required additional therapy with forbidden medicinal products or the medicinal products not specified in the Protocol, such medicinal products may be prescribed in this case. However, Study Sponsor should be notified on the Protocol deviation within 24 hours. In this case, the subject who received forbidden medicinal products or medicinal products not specified in the Protocol may be excluded from the study.

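### Section 5.4.5 ends follow-up of adverse events open at withdrawal that section 8.2.12 requires to be monitored

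*Combined protocol and SAP*

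**What the plan says.** Section 8.2.12 consists of one rule: "All AEs should be monitored until their resolution or stabilization".

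Section 5.4.5 consists of two. The first: "Follow-up of the subjects withdrawn due to a SAE will be performed until its resolution or stabilization". The second: "The subjects withdrawn for other reasons will not be followed".

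The withdrawal reasons in 5.4.2 include "Serious or intolerable AE requiring withdrawal from the study at the investigator's discretion" (item 2), so a non-serious AE can be the reason a subject leaves. Item 5 covers protocol deviations and gives as its example "necessity or performance of additional therapy forbidden by the Protocol". Section 6.2.3 adds that, after treatment of a life- or health-threatening situation, "the subject who received forbidden medicinal products or medicinal products not specified in the Protocol may be excluded from the study".

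Sections 4.3.4.8 and 5.4.3 advise one early withdrawal visit, at which AEs and SAEs are recorded; no later contact is described. Section 8.2.4 sets the SAE recording period: from consent "for up to 30 days after the study product treatment discontinuation or until the last visit whichever is the latter". Under 8.2.6 an "SAE should be reported to Sponsor within 24 hours after the investigator became aware of the SAE".

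**The concern.** The two sections give a site opposite instructions about the same event. The subject most clearly caught is one whose AE was bad enough to end participation but did not meet the seriousness criteria: 8.2.12 says keep monitoring, 5.4.5 says stop.

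At stake is mainly the care and safety information of that subject. Treatment is a single injection of a drug with a half-life of about 10 days, so leaving the study does not end exposure. The AEs of special interest in 8.2.3 include infection, neutropenia and liver injury, whose later course matters clinically. For the data, the possible loss is a later worsening of the event or its outcome.

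**Working it through.** **1. The rules side by side.** The protocol states no figure to reproduce here, so the check is a comparison of text.

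| Situation at withdrawal | 5.4.5 | 8.2.12 | Agree? |
|---|---|---|---|
| SAE open, and it was the reason for withdrawal | follow | monitor | yes |
| Non-serious intolerable AE open, and it was the reason (5.4.2 item 2) | do not follow | monitor | no |
| Non-serious AE open, other reason | do not follow | monitor | no |
| SAE open, other recorded reason (e.g. 5.4.2 item 5) | do not follow | monitor | no |

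The sections agree only in the first row.

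**2. Does follow-up in 5.4.5 mean study visits or the event?** The first sentence of 5.4.5 runs follow-up until the SAE resolves or stabilises, the same end point that 8.2.12 uses. So 5.4.5 is about following the event, and its second sentence denies that to all other withdrawn subjects.

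**3. Does another section settle it?** Sections 4.3.4.8, 5.4.2, 5.4.3, 8.2.4, 8.2.6, 8.2.10 and 8.2.13 were read for this. None ranks the two rules. Section 8.2.13 expressly extends to withdrawn subjects, but only for pregnancy outcomes; AEs have no matching sentence. Section 8.2.10 keeps the outcome of unknown for cases where attempts to reach the subject failed, which is not the same as a planned stop.

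**4. How much exposure remains?** Inputs: half-life 235 h (lower end of the range in section 2.2) to 250 h (section 2.4); median Tmax 96 to 120 h (section 2.2, healthy volunteers). Assumption, not in the protocol: one compartment with first-order absorption. With dosing on Day 1, t = 24 × (day − 1) hours.

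- ke = ln 2 / half-life; ka solves Tmax = ln(ka/ke) / (ka − ke)
- Share of AUC still to come = (ka·e^(−ke·t) − ke·e^(−ka·t)) / (ka − ke)
- Level relative to peak = (e^(−ke·t) − e^(−ka·t)) / (e^(−ke·Tmax) − e^(−ka·Tmax))

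Example, 235 h and 96 h: ke = 0.693147/235 = 0.00295 per hour and ka = 0.02536 per hour. At Day 14, t = 312 h, and the share is (0.02536 × 0.3984 − 0.00295 × 0.0004) / 0.02241 = 45.1%.

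| Half-life / Tmax | AUC to come, Day 3 | Day 14 | Day 28 | Level vs peak, Day 14 | Day 28 |
|---|---|---|---|---|---|
| 235 h / 96 h | 94.3% | 45.1% | 16.7% | 59.8% | 22.2% |
| 235 h / 120 h | 95.5% | 47.6% | 17.7% | 67.2% | 25.2% |
| 250 h / 96 h | 94.5% | 47.1% | 18.6% | 61.4% | 24.2% |
| 250 h / 120 h | 95.7% | 49.4% | 19.5% | 68.5% | 27.2% |

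The same formula gives about 2% at Day 60 and 0.2–0.3% at Day 90. These figures describe exposure. They do not estimate how many events would be missed.

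**The case against.** The strongest reply is that the texts can be read together: 8.2.12 is a general line, 5.4.5 is the specific rule for withdrawn subjects, and the specific usually governs. Section 8.2.4 collects AEs only until the subject completes the study, and 8.2.10 has outcome categories for events still continuing. This is a fair reading, but no section states it. If it is right, it confirms that monitoring of a known open event stops, which is the poorer rule for safety.

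Several points on the other side do stand:

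- **The open-SAE case is narrow.** It needs a site to record a protocol deviation although a life-threatening event led to the forbidden therapy. The Sponsor is told of the deviation within 24 hours (6.2.3), of the SAE within 24 hours (8.2.6), and must agree to the withdrawal (5.4.2 item 5, 10.4). Exclusion is optional.
- **The non-serious case has a partial outlet.** The investigator may class a medically relevant event as an SAE (8.2.5), and 5.4.5 then applies its first sentence if that event caused the withdrawal.
- **The planned tables barely use the lost information.** Section 9.3.4 tabulates AEs by class, term, causality, expectedness and severity, not by outcome. Only a later worsening or newly met seriousness could change a table.
- **The exposure argument fades.** It applies to the first weeks, while the conflict with 8.2.12 runs for the full 12 months.

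Two stronger readings are tempting and not supported. A reader might infer that 5.4.5 also contradicts the 30-day SAE window in 8.2.4. That section sets a recording period and orders no contact, so for withdrawals before Day 31 (Day 1 + 30 days) the two fit together poorly but do not contradict. A reader might also infer that the choice between 80 and 160 mg, which section 2.4 rests on risk-benefit, would be distorted. Nothing in the documents suggests the loss would differ by arm.

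**Conclusion.** The contradiction is real, and it concerns current protocol text. It covers any AE open at withdrawal for a reason other than an SAE: chiefly a non-serious intolerable AE that caused the withdrawal, and more rarely an SAE in a subject with another recorded reason. Followed literally, 5.4.5 ends safety monitoring of an event the site already knows about.

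The number of subjects affected cannot be derived; the documents give no rate. It is probably small and may be zero. The AE that caused the withdrawal is still recorded and counted. The primary hsCRP AUC analysis and the sample size are untouched, and no effect on dose selection is shown. The statement that substantial exposure remains holds for withdrawals in the first weeks only. It rests on the assumed one-compartment model and on healthy-volunteer Tmax values.

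Where a subject recalls consent and refuses contact, follow-up would stop under either rule. Pregnancy is not affected. The point merits correction because the text gives sites conflicting safety instructions and is easily repaired.

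**What to change.** Replace the second sentence of 5.4.5 with: *Unless the subject refuses further contact, any AE or SAE open at withdrawal, whatever the reason for withdrawal, is monitored to resolution or stabilization (8.2.12).*

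Cost: one sentence in an amendment and a few phone contacts per affected subject; no added visits or procedures. Subjects who refuse contact would still not be followed.

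Optional addition: one phone contact at 30 days after dosing for subjects who withdraw earlier. This would make the 8.2.4 SAE window workable for them. It is a new requirement, not the repair of a contradiction, and can be decided separately.
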